### **11.1.3 Visit 3 (Day 7 ±2)**

The following tests and procedures will be performed:

- Checking for concomitant medication
- Inquiring about adverse event and fill an adverse event form if any
- Checking the patient's diary for tinnitus
- The investigator or designee will check the IP and oral corticosteroids diary for compliance.
- Vital signs: blood pressure and heart rate, temperature
- 12-lead digitalized ECG
- Otologic examination and tympanometry
- Audiometric tests: Pure tone audiometry, OAE tests (optional)
- Word and speech recognition Tests

The patient will be asked to complete specific questionnaires:

- Tinnitus and Vertigo presence and Severity (NRS)
- QoL: EQ-5D-5L;
- Tinnitus functional Index (TFI)
- C-SSRS

The patient will be asked to complete a new patient diary for IP and corticosteroid compliance. The patient will be instructed to return his/her treatment carton and diary at the following visit. The patient will be given back the treatment carton to be taken home. The patient will be reminded to record tinnitus presence and intensity in the SSNHL affected ear on a daily basis, and IP and corticosteroid intake. He will be asked to return the diary at the following visit, and to come in a fasting condition and not take the morning IP dose whenever the visit 4 is scheduled in the morning to allow a Pre-dose PK at Visit 4.

### **11.1.4 Visit 4 (Day 14 ±2)**

The following tests and procedures will be performed:

- Checking for concomitant medication
- Inquiring about adverse event and fill an adverse event form if any
- The investigator or designee will check the IP and oral corticosteroids diary for compliance
- Checking the patient's diary for tinnitus
- Otologic examination and tympanometry

- Vital signs: blood pressure and heart rate, temperature
- 12-lead digitalised ECG
- Blood collection for routine hematology and serum chemistry (section 9.2.4)
- Serum sample for prestin and plasma sample for drug concentrations
- Audiometric tests: Pure tone audiometry and OAE tests (optional)
- Word and speech recognition Tests
- Pregnancy test (for WOCBP)

In case rescue medication is administered, please report in the e-CRF

The patient will be asked to complete specific questionnaires:

- Tinnitus and Vertigo Presence and Severity (NRS)
- QoL: EQ-5D-5L;
- TFI
- C-SSRS

The patient will be asked to complete a new patient diary for IP and corticosteroid compliance. The patient will be instructed to return his/her treatment carton and diary at the following visit,

The patient will be instructed to return all used and unused study treatment bottles at the following visit and to come in a fasting condition.

#### **11.1.5 Visit 5: End of Treatment Visit (Day 28±3)**

The following tests and procedures will be performed:

- Checking for concomitant medication
- Inquiring about adverse event and fill an adverse event form if any
- The investigator or designee will count the returned IP tablets
- The investigator or designee will check the oral corticosteroids diary
- Otologic examination and tympanometry
- Complete Physical examination including weight and evaluation of main body systems/regions,
- Vital signs: Blood pressure and heart rate, temperature
- 12-lead digitalized ECG
- Audiometric tests: Pure tone audiometry and OAE tests (optional)
- Word and Speech Recognition Tests
- Blood collection for routine hematology and serum chemistry (section 9.2.4)
- Serum sample for prestin and plasma sample for drug concentrations
- Pregnancy test (for WOCBP)

In case rescue medication has been administered, please report in the e-CRF.

The patient will be asked to complete specific questionnaires:

- Tinnitus and Vertigo Severity (NRS)
- QoL: EQ-5D-5L
- TFI
- C-SSRS

#### **11.1.6 Visit 6 End Study visit (Day 84±3)**

The following tests and procedures will be performed at Visit 6 and in the case of premature withdrawal during the study (i.e. prior to Visit 6):

- Inquiring about adverse event and fill an adverse event form if any
- Checking for concomitant medication
- Physical examination including weight and evaluation of main body systems/regions,
- Vital signs: supine blood pressure and heart rate, temperature
- Otologic examination and tympanometry
- Audiometric tests: Pure tone audiometry and OAE tests (optional)
- Word and Speech recognition Tests
- Pregnancy test (for WOCBP)

The patient will be asked to complete specific questionnaires:

- Tinnitus and Vertigo Severity (NRS)
- QoL: EQ-5D-5L
- TFI

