## 9.6 Accountability and compliance

The date and time of the first intake will be recorded on the eCRF.

The patient will be instructed to return all used and unused investigational kits at every on-site visit. He/she will be provided a diary to record the intake of IP (number of tablets, date and time). The investigator or designee will count the returned tablets and complete the corresponding e-CRF.

The type and dose of corticosteroids will be recorded on the eCRF. The patient will record the intake of corticosteroid in the diary. Corticosteroids intake will be also recorded on the e-CRF, based on the patient's information.

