## 9.10 Concomitant treatment

### 9.10.1 Background therapy

Corticosteroids by oral route (including but not limited to prednisone, methyl prednisolone, dexamethasone) are usually considered as the standard of care (Appendix 6). The guidelines published by the AAO-HNS recommend prednisone for patients with SSNHL within 2 weeks after the diagnosis, with a recommended dose of Prednisone 1 mg/kg/day (max: 60 mg/day), or Methylprednisolone 48 mg/d or Dexamethasone 10 mg/d given as a single dose for 7-14 days, then taper over similar time period. Since there is no harmonization on this clinical practice,

---

each site will be requested to pre-specify the type and dosage regimen of oral corticosteroid that will be given to patients as standard of care. Unless contra-indicated, the pre-specified oral corticosteroids will be prescribed to all patients at a given site. The time, dose and route of administration will be recorded on the e-CRF. The randomisation will be stratified according to the corticosteroid intake. Compliance of the corticosteroids intake will be assessed by the investigator at every on-site visit from the patient diary. Any contra-indication will be recorded on the e-CRF at the sites.

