### 10.2.4 Electrocardiogram (ECG)

A standard digitalized 12-lead electrocardiogram (ECG) will be performed at baseline (Visit 2) prior to randomisation, on Day 7 (Visit 3), Day 14 (Visit 4), and End of treatment visit Day 28 (Visit 5). Each ECG will be triplicated. Ideally at V4 and V5 least one of the PK samples MUST be collected within 15 minutes of the 3rd ECG test being performed.

Heart rate will be recorded from the ventricular rate and the PR, QRS and QTc ( $QTc = QT / [60 / \text{heart rate}]^{1/2}$ ) intervals will be recorded. The digitalized ECG, collected in triplicate, will be managed with a central reading. Corrections of the QT interval will be calculated using Fridericia's and Bazett's formula. Changes from the baseline QT interval will also be assessed.

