### 10.2.5 Laboratory safety

A standard laboratory blood test will be performed at the screening visit (Visit1), on Day 14 (Visit 4), and End of treatment visit Day 28 (Visit 5) also performed in case of Early termination between Visit 2 and Visit 5. Routine serum hematology and chemistry samples will be collected in EDTA tubes and according to the study flow chart. They will be kept at the local

---

laboratory as per laboratory requirements and outlined in the investigator manual which will be available at each investigational site.

The standard laboratory blood test comprises:

- haematology: complete blood count (CBC) including haematocrit, haemoglobin, red blood cell count, white blood cell count with differential count and platelets,
- Serum chemistry including: sodium, potassium, chloride, calcium, phosphorous, urea, creatinine, creatinine clearance (calculated with the Cockcroft-Gault formula for patients <65 years old and CKD-EPI creatinine equation or with MDRD equation for patients ≥65 years old), uric acid, total protein, albumin, lactate dehydrogenase (LDH), Alanine Aminotransferase (ALT), Aspartate Transaminase (ASAT), alkaline phosphatase, GGT and total bilirubin, fasting glycaemia (fasting is not required at baseline), creatine phosphokinase (CPK), triglycerides, cholesterol.
- Glucose (no fasting is needed at screening)
- C Reactive Protein (CRP).
- A urine or blood pregnancy test (in females of childbearing potential) will be performed at the screening visit, on D14 (Visit 4), end of treatment visit (D28 visit 5) and end of study visit (D 84 Visit 6). A subject cannot be included with a positive urine test. Blood sample will be taken for confirmation of the pregnancy status at baseline and end of study visit. In case of positive results, the pregnancy outcome should be reported. For practicability, urine samples may be replaced by blood samples.

No centralized laboratory procedure for laboratory safety is planned. Only local laboratories will be used.

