#### **10.2.7 Suicidality assessment:**

As per FDA guidelines for any neurologic investigational product, a suicidality assessment will be performed via the C-SSRS questionnaires (42) that will be completed at every visit from visit 2 until end of treatment visit (visit 5) by a trained personal. A series of questions about suicidal thoughts and behaviors will be asked. To most quickly and simply identify whether a person is at risk and needs assistance, a minimum of two and a maximum of six questions, depending on the answers will be asked. The patient should answer yes or no to the questions.

The C-SSRS questions use plain and direct language, which is most effective in eliciting honest and clear responses. This scale has been widely used in clinical trials and is translated in many languages. It has been validated by most of health authorities.

Results could trigger decisions about hospitalisation, counseling, referrals, and other actions. If any, an adverse event form should be completed.

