### 10.3 Pharmacokinetic evaluation

Serum samples will be collected for pharmacokinetic (PK) analysis on Day 14 (Visit 4) and End of treatment visit (Visit 5): for more details, please refer to the laboratory manual. Ideally at least one V4 and V5 PK samples MUST be collected within 15 minutes of the 3rd ECG test being performed. Blood samples will be drawn, handled and stored in a secure location as per laboratory requirements, outlined in the laboratory manual which will be available at each investigational site, until shipment. The date and hour of the last drug intake and blood sampling will be recorded.

Several samples will be batched together in the same shipment. The person in charge of the shipment will be contacted by the CRO who will organize samples' shipment. If the site needs to transfer the samples rapidly (due to storage constraint for instance), the CRO should be contacted.

PK samples will be destroyed after the finalization of the complete Clinical Study Report. No further uses of biological samples are planned, i.e. for additional research.

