### 11.3 Subject withdrawal

#### 11.3.1 Removal of subjects from therapy or assessment

In accordance with the current revision of the Declaration of Helsinki and current law, a subject has the right to withdraw from the study at any time for any reason without prejudice to his/her future medical care by the physician or at the institution. The Investigator and Sponsor also have the right to withdraw subjects from the study in the event of intercurrent illness, adverse events, treatment failure, protocol violation, or other reasons. Should a subject (or a subject's legally authorized representative) decide to withdraw, all efforts will be made to follow the patient and to complete and report the observations as thoroughly as possible on the appropriate case report form.

Subjects who discontinue treatment should be assessed in accordance with the assessments/tests specified normally for the end of study visit (V6) if discontinuation occurs after Visit 5 or the end of Treatment Visit (V5) if discontinuation occurs before Visit 5.

Subjects who have been withdrawn from the study cannot be re-included in the study. Their subject number and treatment number must not be re-used. They should not be replaced.

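### Protocol 11.1.6 applies the Visit 6 list to every early withdrawal, omitting the exit ECG, C-SSRS and prestin/PK samples that 11.3.1 requires before Visit 5

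*Protocol*

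**What the plan says.** Three parts of the protocol bear on what is done when a patient leaves early.

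- Section 11.1.6 (Visit 6) gives its own scope. The list is "performed at Visit 6 and in the case of premature withdrawal during the study (i.e. prior to Visit 6"). It covers adverse events, concomitant medication, physical examination, vital signs, otologic examination with tympanometry, audiometry, word and speech tests, pregnancy test, the tinnitus and vertigo scales, EQ-5D-5L and TFI.
- Section 11.3.1 (under Subject withdrawal) divides the exit visit at Visit 5: the Visit 6 tests if the patient discontinues after it, and "the end of Treatment Visit (V5) if discontinuation occurs before Visit 5".
- Section 10.2.5 has its own early-exit rule for the safety laboratory tests, which are "also performed in case of Early termination between Visit 2 and Visit 5".

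The other assessment sections have no such rule. The ECG is done at baseline and "on Day 7 (Visit 3), Day 14 (Visit 4), and End of treatment visit Day 28 (Visit 5"). The C-SSRS is a questionnaire "that will be completed at every visit from visit 2 until end of treatment visit (visit 5"). For PK, "Serum samples will be collected for pharmacokinetic (PK) analysis on Day 14 (Visit 4) and End of treatment visit (Visit 5"). Section 10.4 on prestin likewise names scheduled visits only, and the flow charts in section 4 have no early-withdrawal column.

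**The concern.** For a patient who leaves before Visit 5, two sections name different exit lists. Section 11.1.6 is where site staff look for visit procedures. It states when its list applies and does not refer to 11.3.1, so a site can obey it to the letter and still omit assessments that the protocol requires elsewhere.

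What is at stake is exit safety data. ECG findings and suicidality are both named safety endpoints (6.2.4), and a confirmed QTc above 500 ms is a withdrawal criterion (11.3.2). A missed C-SSRS stays missing, because SAP 6.2.12 rules out imputation for it.

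**Working it through.** No statistical formula applies to the main point. The check compares the two lists, looks for other text that fills each gap, and then asks how many patients could be concerned.

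**1. Compare the lists.** Section 11.1.5 (Visit 5) has 13 procedures and 4 questionnaires, 13 + 4 = 17 items. Section 11.1.6 has 8 procedures and 3 questionnaires, 8 + 3 = 11 items. All 11 are also in the Visit 5 list, so 17 − 11 = 6 items are in Visit 5 only and none is in Visit 6 only.

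**2. Look for other text that restores each of the six.**

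| In Visit 5 only | Required at early exit by text other than 11.3.1? |
|---|---|
| Returned-tablet count | Yes, 9.6: "The patient will be instructed to return all used and unused investigational kits at every on-site visit", and the returned tablets are counted |
| Corticosteroid diary check | Yes, 9.10.1: "Compliance of the corticosteroids intake will be assessed by the investigator at every on-site visit from the patient diary" |
| Haematology and chemistry | Yes, 10.2.5 |
| 12-lead ECG | No |
| C-SSRS | No |
| Prestin and PK samples | No |

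6 − 2 − 1 = 3 items depend on 11.3.1 alone.

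**3. Identify the patients exposed.** Exits prompted by an adverse event or an abnormal value already carry rechecks and follow-up (11.1, the note in 11.3.2, and 12.6). That leaves patients who leave before Visit 5 for another reason. Section 11.3.2 lists at least three: noncompliance, an administrative decision, and the patient's own request unrelated to an intolerable adverse event.

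**4. Work out what such a patient would lack under 11.1.6 alone.** The Visit 3 window opens on Day 7 − 2 = Day 5. A patient who leaves before Visit 3 has no scheduled post-baseline ECG or C-SSRS. One who leaves between Visit 3 and Visit 5 lacks only the exit value. PK sampling starts at Visit 4, whose window opens on Day 14 − 2 = Day 12, so a patient who leaves before Visit 4 has no PK sample.

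**5. Put a number on early leavers.** The documents give no withdrawal rate before Visit 5. The only figure is the 10% dropout allowance for Part 2 (13.1), with no timing: 190 × 0.10 = 19 patients. Two assumptions about timing give a range:

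- dropout spread evenly over 84 days: 19 × 28/84 = 6.3, about 6 patients before Visit 5;
- all dropout before Visit 5: 19 patients.

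This range counts every early leaver. The number affected is the subset that leaves for a reason in step 3 at a site that does not apply 11.3.1. The documents give no figure for that share, so the number affected could be zero.

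**The case against.** The strongest reply is that the protocol already has the right rule in the right place. Section 11.3.1 governs withdrawal and requires the Visit 5 tests. Because the Visit 6 list is contained in the Visit 5 list, a site that does the Visit 5 list satisfies both sections, and nothing in 11.1.6 forbids the extra tests. On this view the defect is a missing cross-reference, and data are lost only if a site overlooks an explicit requirement. It is true that the rules can be met together, and this is why the point is minor. But 11.1.6 sets its own scope, and that scope is too wide for a patient who leaves before Visit 5.

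A second reply is that the sections have different triggers: withdrawal from the study in 11.1.6, discontinuation of treatment in 11.3.1. This does not help, because a patient who leaves before Visit 5 does both. Section 7.6 also counts withdrawal from treatment within the 28 days as treatment discontinuation, and 11.3.1 extends past Visit 5, when treatment is normally over, so it works as an exit rule.

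A third is that 11.3.1 asks for observations on a withdrawing patient to be as complete as possible. That is general and names no test.

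On consequence the objection has more force. SAP 6.2.12 counts a positive C-SSRS answer at any time during double-blind treatment, so answers at Visits 3 and 4 still count when the exit form is missing. ECG analysis is left to a separate plan (SAP 6.2.11) that is not among the documents, so the effect on the QTc results cannot be judged. Prestin is exploratory and PK concentrations are only summarised.

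**Conclusion.** The concern holds as a minor wording error. As written, 11.1.6 prescribes for withdrawals before Visit 5 a list that lacks three assessments required by 11.3.1 and by no other section: ECG, C-SSRS and prestin/PK samples. Two of these serve named safety endpoints.

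The mismatch in the text is certain. Any loss of data is conditional: it needs a withdrawal before Visit 5, not driven by an adverse event or abnormal value, at a site that does not also apply 11.3.1. The 6 to 19 early leavers in Part 2 rest on the 10% allowance and on assumed timing, and only some of them, possibly none, would be affected. Audiometry is in both lists, so the primary endpoint is unaffected. Safety is analysed descriptively (13.5.4), and sample size, power and type I error are not involved.

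**What to change.** Replace the opening sentence of 11.1.6 with wording such as: *These assessments are done at Visit 6 and when a patient withdraws after Visit 5. A patient who withdraws before Visit 5 has the Visit 5 assessments in 11.1.5, as 11.3.1 requires.*

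The change is wording only and adds no test, since 11.3.1 already asks for the Visit 5 assessments. The substantial amendment that section 14.4 foresees before the pivotal part can carry it. The benefit falls mainly in Part 2, because SAP section 4 reports that Part 1 had already reached the sample size of its second interim look.

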#### **11.1.7 Unscheduled Visit: Visit 99**

In case of adverse event, abnormal values or dispensation of a replacement IMP kit, an additional visit may be needed to repeat the test or document an adverse event or to dispense a new IMP kit.

### 11.2 Definition of source data

The list of information considered to be raw data which must be shown in the subject's file are listed in Appendix 5.

The results of certain investigations or assessments included on the e-CRF may be considered to be raw data. Direct e-CRF data entries, if any, should be defined during initiation visits at the latest, by the investigational team and implemented for the rest of the study.

### 11.3 Subject withdrawal

#### 11.3.1 Removal of subjects from therapy or assessment

In accordance with the current revision of the Declaration of Helsinki and current law, a subject has the right to withdraw from the study at any time for any reason without prejudice to his/her future medical care by the physician or at the institution. The Investigator and Sponsor also have the right to withdraw subjects from the study in the event of intercurrent illness, adverse events, treatment failure, protocol violation, or other reasons. Should a subject (or a subject's legally authorized representative) decide to withdraw, all efforts will be made to follow the patient and to complete and report the observations as thoroughly as possible on the appropriate case report form.

Subjects who discontinue treatment should be assessed in accordance with the assessments/tests specified normally for the end of study visit (V6) if discontinuation occurs after Visit 5 or the end of Treatment Visit (V5) if discontinuation occurs before Visit 5.

Subjects who have been withdrawn from the study cannot be re-included in the study. Their subject number and treatment number must not be re-used. They should not be replaced.

#### 11.3.2 Withdrawal criteria

The subjects could withdraw from the study if they decided to do so, at any time and irrespective of the reason, or this could be the Investigator's decision. All drops out must be documented and the investigator must give the reason (adverse event, subject request, other reason...).

All adverse events, both serious and non-serious, that result in the subject's withdrawal from the study (either by subject request or Investigator decision) must be reported to the CRO (Sensorion designee) within 24 hours for serious events, and within 7 days for non-serious events.

Subjects may be removed from the study by the investigator or the sponsor, if one or more of the following occurs:

- Any serious or severe (CTCAE GRADE 3) related adverse event will lead to permanent treatment discontinuation
- Adverse events of lesser grade should be evaluated in the context of concomitant clinical and laboratory findings and, in the judgment of the Investigator and responsible medical officers, may be cause for temporary or permanent discontinuation of treatment for an individual subject. If interruption of treatment for an individual subject is required due to adverse events more than once during the trial, then the subject will be withdrawn from further treatment.
- Significant laboratory abnormalities
  - Confirmed ALT > 5 ULN (or > 3 times baseline value if ALT > ULN at baseline) or in case of confirmed ALT >3 ULN and total bilirubin >2 ULN (unless the patient has Gilbert's disease documented by genetic testing)
  - Confirmed, non-rapidly reversible, increase in serum creatinine  $\geq$  1.7 mg/dL (150  $\mu$ mol/L) or rapid decrease in creatinine clearance reaching < 50 ml/min-
  - Confirmed rhabdomyolysis (CPK should be controlled in case of suspicion)
  - Confirmed decline in hemoglobin of > 3 g/dL compared to baseline and hemoglobin

level grade 1 (< LLN - 10 g/dL) or higher of CTCAE terminology

- Confirmed platelet count < 100,000 cells/mm^3 with or without spontaneous bleeding
- Confirmed decline in total white blood cell count of > 50% compared to baseline and white blood cell count grade 1 or higher of CTCAE terminology (< LLN - 3000/mm^3)
- Confirmed neutrophil count < 1500/mm^3 with or without signs of infection
- Confirmed decline in lymphocyte count of > 50% compared to baseline and lymphocyte count grade 2 (< LLN - 500/mm^3) or higher of CTCAE terminology
- Confirmed elevated INR grade 3 (> 2.5 x ULN) or higher of CTCAE terminology
- Confirmed QTc > 500 ms

Note: Any abnormal laboratory value or ECG parameter will be immediately rechecked for confirmation before making a decision of permanent discontinuation of IMP for the concerned patient.

- Any adverse events, per investigator judgment, that may jeopardize the patient safety
- Any patient with a temporary discontinuation for safety reasons that is greater than or equal to 10 consecutive days from last IMP administration
- Any treatment unblinded by the Investigator
- Noncompliance with study protocol by the subject.

Decision by the Investigator or Sponsor that termination is in the subject's best medical interest or administrative decision for a reason other than that of an adverse event.

- Request for withdrawal by the subject for reasons other than an intolerable adverse event.
- Lost to follow-up: For subjects considered lost to follow-up, the e-CRF must be filled in up to the last visit performed. The Investigator should make every effort to re-contact and to identify the reason why the subject failed to attend the visit and to determine his/her health status.

